## SYNOPSIS

**Title of study:** Open-label, Nonrandomized, Single-dose, Parallel-group, Safety, Tolerance, and Pharmacokinetic Study of LOXO-292 Administered to Fasted Hepatically Impaired Male and Female Subjects and Fasted Matched-control Healthy Subjects

**Objectives:**

The objectives of this study are:

- To evaluate the pharmacokinetic (PK) profile of LOXO-292 in subjects with impaired hepatic function compared to matched-control healthy subjects;
- To evaluate safety and tolerability of LOXO-292 in subjects with impaired hepatic function and matched-control healthy subjects.

**Study design:**

This study will be an open-label, nonrandomized, multi-center, single-dose, parallel-group, safety, tolerability, and PK study of LOXO-292 administered at a dose of 160 mg in fasted matched-control healthy males and females with normal hepatic function compared to fasted, hepatically impaired subjects.

Subjects will be recruited in this study so that up to 24 subjects with hepatic impairment (up to 8 subjects within each of the mild, moderate, and severe impairment groups, per Child-Pugh [CP] classification – assessed at Screening and Check-in [Day -1]), and approximately 8 to 16 subjects with normal hepatic function are enrolled. Subjects will be enrolled within the following groups based on their CP score at Screening and assuming no change in underlying hepatic status at Check-in (Day -1) as judged by the Investigator (or designee), the Covance Medical Monitor, and the Sponsor:

- Group 1: Matched-control healthy subjects with normal hepatic function;
- Group 2: Subjects with mild hepatic impairment (CP Class A, score of 5 or 6);
- Group 3: Subjects with moderate hepatic impairment (CP Class B, score of 7 to 9);
- Group 4: Subjects with severe hepatic impairment (CP Class C, score of 10 to 15).

A parallel design strategy will be adopted for the hepatic impairment groups, with interim reviews of safety data after the first 4 subjects from Group 2 (mild hepatic impairment subjects), the first 4 subjects from Group 3 (moderate hepatic impairment subjects), and the first 2 subjects from Group 4 (severe hepatic impairment subjects) are enrolled and have completed all study-related assessments including the Follow-up phone call. Enrollment and dosing for remaining subjects in any group may occur after the interim data for that group are reviewed and the Covance Medical Monitor, Investigator (or designee), and Sponsor agree it is safe to proceed with dosing. If available, PK data and matched-control healthy subject data may also be used during the interim review.

Each matched-control healthy subject (Group 1) will be demographically matched (1:1) by age ( $\pm$  10 years), body mass index (BMI;  $\pm$  20%), and sex to the enrolled hepatic impairment subject(s). Should another hepatic impairment subject be identified with whom an already enrolled healthy subject is demographically matched, the healthy subject may also be matched with that impaired subject as long as the impaired subject is in a different hepatic impairment group. Each subject with normal hepatic function may be matched with up to 1 subject within each hepatic impairment group.

To assess their eligibility to enter the study, potential subjects will be screened within 28 days (Days -29 to -2) and be admitted to the clinical site on Day -1 (Check-in). Replacement subjects may be enrolled only if deemed necessary by the Sponsor.

Subjects will be confined at the clinical site from the time of Check-in (Day -1) until EOT on Day 11 upon completion of all PK and safety assessments or ET if the subject discontinues. A Follow-up phone call will occur 7 days ( $\pm$  2 days) after EOT or ET.

On the morning of Day 1, after at least a 2-hour fast, an oral dose of 160 mg LOXO-292 administered as two 80-mg capsules will be given with 240 mL water. No food will be allowed for up to 1 hour postdose. Glucose tablets may be administered as needed for treatment of hypoglycemia.

In this study, physical examinations (PEs), 12-lead electrocardiograms (ECGs), vital signs, How Do You Feel? inquiries, clinical chemistry panel, coagulation parameters, complete blood count (CBC), and urinalysis (UA; [Appendix 2](#)) will be performed at Screening and at specified times during the study (for specific timepoints and details on each study variable, refer to [Appendix 5](#)). Adverse events (AEs) and serious adverse events (SAEs) will be collected beginning at informed consent. AEs will be reported throughout the study (ie, from signing of the Informed Consent Form [ICF] until End of Study [EOS], or until Early Termination [ET] if the subject discontinues from the study and does not complete a follow-up call), either as subject medical history (if the event is reported as beginning prior to signing of the ICF or if the event occurs prior to study drug administration on Day 1 and is assessed as not related to study procedures by the Investigator [or designee]) or as AEs (if the event occurs after signing of the ICF but prior to study drug administration on Day 1 and is assessed as related to study procedures by the Investigator [or designee], or if the event occurs after study drug administration on Day 1 through End of Treatment [EOT] or ET regardless of relationship to study drug). From EOT or ET through EOS, only AEs assessed as related to study drug by the Investigator (or designee) are to be reported. All SAEs that develop from the time of ICF signing until EOS (or ET, if the subject discontinues from the study and does not complete a follow-up call) are to be reported.

Study Completion is defined as the time of the last subject's Follow-up phone call.

**Interim review:**

Interim reviews of safety data will be conducted for each group when the first 4 subjects from Group 2 (mild hepatic impairment subjects) are enrolled and have completed the study, when the first 4 subjects from Group 3 (moderate hepatic impairment subjects) are enrolled and have completed the study, and when the first 2 subjects from Group 4 (severe hepatic impairment subjects) are enrolled and have completed the study. These safety data will include AEs and SAEs, vital signs, PEs, ECGs, and clinical laboratory tests. If available, PK data and matched-control healthy subject data may also be used during the review. Enrollment and dosing for remaining subjects in any group may occur after the interim data for that group are reviewed and if the Covance Medical Monitor, Investigator (or designee), and Sponsor agree it is safe to proceed with dosing.

Following the interim review of safety data for each group, the dose level may be decreased for the remaining subjects in any group pending discussion and agreement between the Covance Medical Monitor, Investigator (or designee), and/or Sponsor. If dose is decreased, it will also be decreased for the impaired subjects' respective matched-control healthy subjects.

**Number of subjects:**

A total of up to 24 subjects with hepatic impairment (up to 8 subjects with mild impairment, up to 8 subjects with moderate impairment, and up to 8 subjects with severe impairment, per CP classification) and approximately 8 to 16 matched-control healthy subjects with normal hepatic function will be enrolled in the study with the goal of having at least 6 subjects from each hepatic impairment group and at least 6 subjects with normal hepatic function complete the study. Subjects who withdraw or drop out of the study may be replaced if deemed necessary by the Sponsor.

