**Sample size:**

The sample size chosen for this study was based upon precedent set by other PK studies of similar nature and was not based on power calculations to detect statistically significant differences among groups. At least 6 subjects each per hepatic function group are planned to complete the study. This is considered a sufficient sample size to evaluate the PK of LOXO-292 under various degrees of hepatic function. If necessary, as determined by the Sponsor, subjects who fail to complete the treatment or have insufficient PK data may be replaced.

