### 3. INVESTIGATIONAL PLAN

#### 3.1. Overall Study Design and Plan

This study is an open-label, nonrandomized, multi-center, single-dose, parallel-group study to determine the PK, safety, and tolerability of LOXO-292 administered orally at a dose of 160 mg to fasted adult males and females with mild, moderate, or severe impaired hepatic function and healthy subjects with normal hepatic function. Hepatic function will be classified based on the CP classification of hepatic impairment (Table 1).

Subjects will be recruited in this study so that up to 24 subjects with hepatic impairment (up to 8 subjects with mild impairment, up to 8 subjects with moderate impairment, and up to 8 subjects with severe impairment, per CP classification – assessed at Screening and verified at Check-in [Day -1]) and approximately 8 to 16 subjects with normal hepatic function are enrolled, with the goal of having at least 6 subjects from each hepatic impairment group and at least 6 subjects with normal hepatic function complete the study. Subjects will be enrolled within the following groups based on their CP score at Screening and Check-in (Day -1) as judged by the Investigator (or designee), Covance Medical Monitor, and Sponsor:

- **Group 1:** Matched-control healthy subjects with normal hepatic function;
- **Group 2:** Subjects with mild hepatic impairment (CP Class A, score of 5 or 6);
- **Group 3:** Subjects with moderate hepatic impairment (CP Class B, score of 7 to 9);
- **Group 4:** Subjects with severe hepatic impairment (CP Class C, score of 10 to 15);

A parallel design strategy will be adopted for the hepatic impairment groups. An interim review of the safety data will be conducted as detailed in [Section 8.2](#).

[figure not shown]
Each matched-control healthy subject (Group 1) will be demographically matched (1:1) by age ( $\pm 10$  years), BMI ( $\pm 20\%$ ), and sex to the completed hepatic impairment subject(s). Should another hepatic impairment subject be identified with whom an already enrolled healthy subject is demographically matched, the healthy subject may also be matched with that impaired subject as long as the impaired subject is in a different hepatic impairment group. Each subject with normal hepatic function may be matched with up to 1 subject within each hepatic impairment group.

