## **4. SELECTION OF STUDY POPULATION**

Up to 8 subjects will be enrolled into each hepatic impairment treatment group to have at least 6 subjects from each group complete the study. Up to 16 subjects will be enrolled into the matched-control healthy subject group to have at least 6 healthy subjects matched to each hepatic impairment treatment group complete the study. Healthy control subjects will be matched demographically to hepatically impaired subjects as noted in [Section 3.1](#).

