### **8. SAMPLE SIZE AND DATA ANALYSIS**

#### **8.1. Determination of Sample Size**

The sample size chosen for this study was based upon precedent set by other PK studies of similar nature and was not based on power calculations to detect statistically significant differences among groups. Six subjects each per hepatic function group are planned to complete the study. This is considered a sufficient sample size to evaluate the PK of LOXO-292 under various degrees of hepatic function.

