10 STATISTICAL METHODOLOGY

10.1 General

Data listings will be provided for the All Subjects Population. Summary statistics and statistical analyses will be performed for subjects included in the relevant analysis populations (Safety/PK).

For continuous data, summary statistics will include the arithmetic mean, arithmetic standard deviation (SD), median, minimum, maximum, and number. For log-normal data (eg, the PK parameters: areas under the concentration-time curve [AUCs] and maximum observed concentration [Cmax]), the geometric mean and geometric coefficient of variation (CV%) will also be presented. For categorical data, frequency counts and percentages will be presented. Data listings will be provided for all subjects up to the point of withdrawal, with any subjects

excluded from the relevant population highlighted. For the calculation of summary statistics and statistical analysis, unrounded data will be used.

Missing values will not be imputed.

Data analysis will be performed using SAS® Version 9.4.

Analysis Data Model (ADaM) datasets will be prepared using Clinical Data Interchange Standards Consortium (CDISC) ADaM Version 2.1, and CDISC ADaM Implementation Guide Version 1.1. Pinnacle 21 Community Validator Version 2.2.0 will be utilized to ensure compliance with CDISC standards.

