10.4.2 Primary Analysis

To evaluate the effect of hepatic function group on the PK of a single dose of LOXO-292, paired t-test will be performed for each hepatic impairment group versus the normal group with respect to 1 to 1 matching. The 1 to 1 matching comparisons of interests include:

- Subjects with severe hepatic impairment versus healthy matched control subjects.

- Subjects with moderate hepatic impairment versus healthy matched control subjects.
- Subjects with mild hepatic impairment versus healthy matched control subjects.

Since the comparison groups of subjects are independent in terms of degrees of hepatic impairment and dependent based on the matching criteria, paired Proc ttest in SAS will be used for this comparison on the natural log transformed PK parameters (AUC_{0-t}, AUC_{0-∞}, and C_{max}). The 90% confidence interval for the ratio between each level of impaired hepatic function versus the matched-control healthy subject group will be presented. The normality assumption will be explored to ensure no major deviation to the assumption exists. The corresponding results along with any outliers will be evaluated and can be included in the CSR appendix as needed. Any major outliers will be investigated case by case and determine the appropriate action on how to handle them.

Example SAS code:

```
proc ttest data= logpk alpha=0.1;  
by paramcd;  
paired normal*impairment;  
run;
```

where;

paramcd = categorical variable to indicate different PK parameters

impairment = natural log-transformed PK parameters for the subjects with hepatic impairment

normal = natural log-transformed PK parameters for the healthy matched controlled subjects

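### Should the completion targets be restated as PK-evaluable matched pairs, the unit of the primary paired analysis?

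*Protocol*

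**What the plan says.** The size targets appear in several places, all as numbers of subjects who complete:

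- Protocol Synopsis, Number of subjects (repeated in Section 3.1): "at least 6 subjects from each hepatic impairment group and at least 6 subjects with normal hepatic function complete the study".
- Protocol Synopsis, Sample size: "At least 6 subjects each per hepatic function group are planned to complete the study".
- Protocol 8.1, and SAP Section 8 in the same words: "Six subjects each per hepatic function group are planned to complete the study".
- Protocol Section 4, for the controls: "at least 6 healthy subjects matched to each hepatic impairment treatment group complete the study".

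Enrolment is up to 8 in each impairment group and about 8 to 16 controls. One control may serve up to one subject in each impairment group (Protocol 4.7).

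The wording on who is matched differs. The Synopsis and SAP Section 6 match controls by age, BMI "and sex to the enrolled hepatic impairment subject(s". Protocol 3.1 has "and sex to the completed hepatic impairment subject(s".

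For the analysis, SAP 10.4.2 states that a "paired t-test will be performed for each hepatic impairment group versus the normal group with respect to 1 to 1 matching", on log-transformed AUC0-t, AUC0-∞ and Cmax, with a 90% interval for each ratio. SAP 10.1 adds: "Missing values will not be imputed". SAP 10.4.3 also plans an ANCOVA on all subjects with group, sex, age and BMI. The Protocol Synopsis (Sample size) and Section 4.5 let the sponsor replace subjects who do not complete treatment or whose PK data are insufficient.

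**The concern.** The precision of each primary comparison depends on its number of evaluable pairs, and no target or replacement rule is expressed in that number. If a control and an impaired subject from different pairs are lost, two pairs go but each group loses only one completer. A group can therefore meet its target of six while its comparison rests on five pairs, or occasionally four.

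Completion is also not the same as having the parameter. Under SAP Section 9 a completer may be left out of the analysis for early emesis. Under SAP 10.3.3 AUC0-∞ is not calculated if the adjusted R² is below 0.7. Conversely, samples from non-completers are assayed and may still contribute a pair.

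The targets also look inconsistent. Six controls in total is a weaker demand than six controls matched to each impairment group, unless every control is shared across all three. Matching to enrolled subjects also gives a different set of pairs from matching to completed ones. At stake is the width of the intervals in a study meant to inform dosing recommendations in hepatic impairment.

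**Working it through.** The plan's figure of six cannot be re-derived: Protocol 8.1 and SAP Section 8 say that it follows precedent and give no SD, effect size or power. The check is therefore how far the pair count can fall, how often, and what that costs.

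**Floor.** With 8 matched pairs and 6 completers on each side, at most 2 pairs are broken from the control side and 2 from the impaired side. Intact pairs lie between 6 + 6 − 8 = 4 and 6.

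**Which reading of the protocol applies.** Section 4 asks for six completing controls matched to each impairment group and says the matching is as in Section 3.1. Section 3.1 matches to completed impaired subjects. Together they give about 6 completer pairs per comparison. The floor of 4 needs either the Synopsis count of controls or the Synopsis wording on enrolled subjects.

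**How often.** Assumptions, not figures from the documents: each subject independently lacks the parameter with probability p; 8 controls are shared by all three groups; there are 8 subjects per impaired group; nobody is replaced. Evaluable subjects in a group follow Bin(8, 1 − p). Pairs in a comparison follow Bin(8, (1 − p)²), with mean 8(1 − p)². Exact enumeration gives:

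| | p = 5% | p = 10% | p = 15% |
|---|---|---|---|
| Mean pairs per comparison | 7.2 | 6.5 | 5.8 |
| One comparison, both groups with at least 6 evaluable: fewer than 6 pairs | 2.4% | 11.5% | 23.9% |
| Same condition: 4 or fewer pairs | 0.1% | 1.3% | 3.8% |
| All four groups with at least 6 evaluable | 97.7% | 85.6% | 64.1% |
| Given that: any of the three comparisons below 6 pairs | 6.2% | 25.2% | 45.5% |

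**What a shortfall costs.** The half-width of the 90% interval on the log scale is t(0.95, n − 1) · σ · √(2/n), with no within-pair correlation:

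- n = 6: 2.015 × √(2/6) = 1.163σ
- n = 5: 2.132 × √(2/5) = 1.348σ, which is 1.348/1.163 = 1.16 times as wide
- n = 4: 2.353 × √(2/4) = 1.664σ, which is 1.664/1.163 = 1.43 times as wide

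A within-pair correlation r multiplies all three by √(1 − r), so the ratios do not change. With σ = √ln(1 + CV²), the interval is the estimate multiplied and divided by these factors:

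| Assumed CV | 6 pairs | 5 pairs | 4 pairs |
|---|---|---|---|
| 30% | 1.41 | 1.49 | 1.63 |
| 40% | 1.57 | 1.68 | 1.90 |
| 60% | 1.91 | 2.11 | 2.52 |

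**What restating the target would add.** Without replacement, all three comparisons reach 6 pairs in 92, 64 and 35% of trials at the three loss rates. Replacing each lost control once, with the same matches and the same loss rate, gives 98, 87 and 65% for 8p = 0.4, 0.8 and 1.2 extra controls on average. Replacing lost subjects once on both sides gives over 99.9, 99.9 and 98.9%; this assumes that replacements do not count towards the 8 per group, on which the protocol is silent. These gains come from replacements that the protocol already allows, with room up to 16 controls. A pair-based target would only prompt their use, and that increment cannot be isolated.

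**Likely loss rate.** Subjects are confined from Day −1 to Day 11 and take one supervised dose. Sampling runs to 240 h against a half-life of about 24 h in healthy subjects, or 240/24 = 10 half-lives, so a poor terminal fit should be uncommon, at least in controls. The R² rule does not affect Cmax or AUC0-t. The low end of the range is the more plausible.

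**The case for a change.** The strongest case for a change is that even a number taken from precedent needs a unit; otherwise the sponsor cannot tell when it has been met. The SAP names the paired test as primary, says that it supersedes the protocol's statistical considerations, and treats the ANCOVA as additional. It does not carry over the analysis of variance that the Synopsis offers where 1:1 matching is not achieved. Nothing directs the sponsor to count pairs: losing two controls and two impaired subjects from other pairs leaves every count of six met and four pairs in that comparison. Restating the goal would cost a few lines of text and about one extra control, or up to three times that if one replacement cannot match all the lost control's partners.

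Much of this stands. No passage sets a number of evaluable pairs, enrolled and completed are different words, and the arithmetic is right. It does not show that the plan misleads. Six and at least six are compatible, and the Section 4 target is stricter than the Synopsis one, not opposed to it: meeting the former meets the latter for controls. Counting subjects per group also suits the ANCOVA that Protocol 8.5 specifies and the SAP keeps. The shortfall figures describe a trial in which the sponsor never uses the replacement provision it has.

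**Conclusion.** No change to the plan is called for. Followed as written, it yields a valid paired comparison on whatever pairs are evaluable, and an ANCOVA that uses every subject with the parameter. Fewer pairs widen the interval, which shows the loss openly; they do not bias the estimate as long as loss is unrelated to exposure. No stated size, power or precision is missed, because none beyond a goal of about six by precedent is claimed.

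For one comparison the chance of falling below six pairs while both groups have six evaluable subjects is 2.4% at 5% loss and 23.9% at 15%. The usual consequence is five pairs and an interval 16% wider; four or fewer pairs, with an interval at least 43% wider, occur in 0.1 to 3.8%. These frequencies rest on assumed independent loss, fully shared controls and no replacement; the width ratios need no assumed CV. The difference between enrolled and completed is a slip of wording, and Section 4's reference to Section 3.1 points to completed. The number of pairs behind each interval is something analysts will report in any case. The only operative effect of a pair target would be a few more controls, under discretion the sponsor already holds.

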**Diagnosis and main criteria for inclusion:**

Male subjects and female subjects of nonchildbearing potential, between 18 and 65 years of age, inclusive, at Screening, and within BMI range 18.5 to 40.0 kg/m^2, inclusive. Subjects will be in good general health, except for additional specific inclusion criteria related to subjects with hepatic impairment, based on medical history, PE findings, vital signs, ECG, and clinical laboratory tests at Screening and Check-in (Day -1), as determined by the Investigator (or designee).

**Investigational products, dose, and mode of administration:**

LOXO-292 will be supplied by Loxo Oncology as 80-mg and 20-mg capsules for oral administration.

Subjects will receive a single dose of LOXO-292, given orally as two 80-mg capsules. If dosing is decreased following the interim review of safety data, subjects will be given appropriate doses using a combination of 80-mg and 20-mg capsules.

